4.3 Participant Inclusion Criteria

Inclusion Criteria:

- Age 55 years and older.
- Healthy (see exclusion criteria below).
- Able to understand the study risks and procedures, and consent to participate in the study.
- Able to read and speak English.

4.4 Participant Exclusion Criteria (Screening Visit)

Exclusion Criteria:

- History of diabetes (requiring any medical treatment other than diet and exercise) or fasting plasma glucose > 126 mg/dl or HbA1c > 6.5 %.
- History of hypoglycemia.
- BMI > 35 kg/m².
- Creatinine clearance less than 60 ml/min as measured by GFR.
- Glucosuria
- History of anemia within the past 6 months or Hgb <11.0 mg/dL for women and Hgb <12.5 mg/dL for men.
- Current steroid use or steroid use within 90 days of screening, excluding eye drops.
- Currently taking loop diuretics (Lasix, for example).
- Participant presently following a calorie restriction diet, low carb/high fat diet.
- HIV virus infection

- Hepatitis B infection, as evidenced by a positive HBsAG at screen visit.
- Hepatitis C infection that has not been treated. (The screen blood work must show HCV RNA quantitative is not detectable).
- Active infection/fever that may cause changes in glucose metabolism.
- Known allergy to sGLT2 inhibitors in the past.
- Thyroid dysfunction that is not controlled or treated. This will be determined by Free T3, T4, Free T4 or TSH not within MedStar Harbor Hospital laboratory normal ranges for this pilot study.
- Adrenal dysfunction as determined by a cortisol level not within the normal range for MedStar Harbor Hospital Laboratory for this pilot study.
- Kidney or liver disease, (GFR < 60 mL/min/1.73 m² and/or liver enzymes not within normal ranges for MedStar Harbor Hospital Laboratory for this pilot study.
- Severe gastrointestinal diseases such as Crohn's disease or ulcerative colitis requiring continuous treatment.
- History of severe pulmonary disease such as chronic obstructive pulmonary disease (COPD) or asthma requiring continuous medication use.
- Patients with known, or evidence of, peripheral vascular disease.
- History of chronic urinary tract infections.
- History of recurrent or recent dehydration in the past year.
- History of recurrent or recent vaginal yeast infection.
- Alcohol intake greater than 30 grams (drink more than 2 beers OR equivalent per day).
- History of severe psychiatric conditions associated with behavioral problems or requiring chronic medical treatment.
- Poor venous access.
- Inability to walk 2,000 steps
- Donation or loss of 400 mL or more of blood within 56 days prior to and subsequent to screening.
- Participation in another study in the past 30 days, in which a study drug was administered.
- Currently participating in another study unless the investigator feels it would not interfere with the study.
- History of a medical condition or any other reason that, in the opinion of the investigator, will make participation in this study unsafe.
- Blood work or urine tests that are not considered by the study physician to be in an acceptable range for the study.
- Metal implants and devices incompatible with 3T Magnetic Resonance Imaging (MRI), or another contraindication to MRI.

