6.1 Clinical Evaluations and MRI/MRS

Medical History and General Physical Examination

Participants receive a standardized physical exam and medical evaluation to include vital signs. Review of concomitant medications. This evaluation is required for study participation.

Body Measurements

Height and weight will be measured. These measurements are required for study participation.

Vital signs/Orthostatic blood pressures

This will be done to monitor for any problems of potential hypotension or dehydration.

Blood samples

Blood work for clinical chemistry, hematology, lipids, oxysterols, lipidomics, and exosomes will be done along with frequent blood sampling for hormones and ketones. An intravenous catheter will be placed for frequent sampling.

Safety Labs

Participants will have a fasting CMP/Lipid Panel on Day 1 of Visits 1, 2 and 3. On Visits 2 and 3 they will also have a CBC to monitor hemoglobin and hematocrit levels. Should a participant have a decrease of greater than 10% from the screening visit, the number of frequent blood draws would be decreased to every 2 hours. Therefore, the amount of blood taken on that visit would be approximately 130 ml (8.8 tablespoons).

Continuous Glucose Monitor (CGM)

The *Free Style Libre Pro* Continuous Glucose Monitor (CGM) device will be placed to measure interstitial glucose concentrations on Visits 1, 2 and 3. At the end of Visits 1 and 2 participants will wear the device until they return for Visits 2 and 3. The device will be removed at the end of Visit 3. The monitor consists of a small sensor that is inserted with a small needle and measures glucose levels just underneath the skin on the abdomen or the arm. The monitor will be inserted by the staff and the participant will be trained on wearing the device and who to call with questions or problems. A transmitter sends data wirelessly to the receiver. Once completed, data will be downloaded from the device to secure NIA servers.

Activity Monitor

On the evening of Day 1, participants will be given an activity monitor to wear on their wrist and will be instructed to walk approximately 2,000 steps. This will be done to try and keep activity levels similar in the 20 participants.

Study Medication

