7.1 Potential Risks

Risks of Blood Drawing and Intravenous (I.V.) insertion: The total amount of blood taken during a screening visit is up to 30 milliliters (ml) or 2 tablespoons. The total amount taken for Visits 1, 2 and 3 will be about 504 ml or 34 tablespoons. Participants may experience some discomfort and/or bruising at the site of needle entry. There is a remote chance of fainting or infection. The I.V. may need to be inserted if unable to obtain frequent blood samples.

Risk of Stored Samples: The greatest risk from the use of stored samples is the unplanned release of information from medical records. The chance that this information will be given to an unauthorized person without the participant's permission is very small. We will not enter any experimental information (research results) into any other medical record and we will not release information to a third party unless specifically authorized by the participant. Possible problems with the unplanned release of information include discrimination when applying for insurance and employment. Some problems may occur if a participant discloses information or he or she agrees to have his or her medical records released.

Risk of Hepatitis Virus B, hepatitis virus C, and human immunodeficiency virus (HIV) Testing: This study involves a number of blood tests that require the subject's blood be tested for blood-transmitted diseases such as hepatitis virus B, hepatitis virus C, and human immunodeficiency virus (HIV). If the participant is infected with HIV, hepatitis B (positive HBsAG) or C (HCV RNA quantitative is detectable), he/she will not be able to participate in this study. We will tell the subject what the results mean, how to find care, how to avoid infecting others, how we report these infections, and the importance of informing any partners of possible risk.

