11.2 Safety Monitoring Plan

All protocols at the NIA follow the NIA Data and Safety Monitoring Plan. This includes using the Level of Risk Assessment Monitoring Guidelines that has been established for the NIA following NIH rules and regulations to ensure good clinical practices in the conduct of clinical research. Participants will be informed about new information from this or other studies that may affect their health, welfare, or willingness to stay in this study.

12 Statistical Considerations

This is a pilot study therefore no power calculation can be done.

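### The haemoglobin exclusion limits in Section 4.4 are printed in mg/dL, so the fixed laboratory arm of the anaemia criterion excludes nobody as written; the practical weight is minor

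*Combined protocol and SAP*

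**What the plan says.** The anaemia exclusion in Section 4.4 has two arms. One is history, introduced by "History of anemia within the past 6 months or Hgb". The other is a fixed laboratory limit by sex: "Hgb <11.0 mg/dL for women and Hgb <12.5 mg/dL for men". The unit is printed twice, once for each sex. No other section states a haemoglobin limit or a haemoglobin unit.

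Three further provisions bear on the point:

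- Section 4.4 also has a discretionary laboratory exclusion: "Blood work or urine tests that are not considered by the study physician to be in an acceptable range for the study". A complete blood count is part of screening (Sections 5.2 and 6.2.1), so haemoglobin falls within it.
- Section 6.1 (Safety Labs) repeats the blood count at Visits 2 and 3 and makes sampling less frequent on this trigger: "Should a participant have a decrease of greater than 10% from the screening visit".
- Section 7.1 gives the blood volumes. For screening: "The total amount of blood taken during a screening visit is up to 30 milliliters (ml) or 2 tablespoons". For the study visits: "The total amount taken for Visits 1, 2 and 3 will be about 504 ml or 34 tablespoons".

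**The concern.** Haemoglobin in living people is measured in grams per decilitre, thousands of times larger than the milligram figures printed here. The limit is an operative eligibility rule and not background text, so its literal meaning matters. As printed, it can never be met. The sponsor chose a fixed entry limit for each sex, and the written rule does not deliver it.

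What is at stake is participant protection and clean conduct, not inference. The study takes repeated blood samples, and Section 4.4 itself treats blood loss as relevant by excluding people with a recent donation or loss of 400 mL or more. If staff silently read the limit in another unit, they apply a criterion that differs from the approved text.

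**Working it through.** **Inputs.** Limits of 11.0 mg/dL (women) and 12.5 mg/dL (men), Section 4.4. Blood volumes of up to 30 ml at screening and about 504 ml for Visits 1 to 3, Section 7.1. Reduced-sampling volume of about 130 ml per visit, Section 6.1. Sampling schedule, Section 5.3. Conversion: 1 g/dL = 1000 mg/dL.

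**1. Blood volume.** The protocol does not print a total. Adding its two figures gives 30 + 504 = 534 ml. This is an upper figure, because the first term is a maximum and the second is approximate.

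**2. Is 504 ml the three-visit total or a per-visit amount?** Assume an equal split and a volume proportional to the number of draws.

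- Per visit: 504 / 3 = 168 ml.
- Post-baseline draws: 2 + 1 + 8 + 4 + 2 + 1 + 4 = 22, or 23 with baseline.
- Two-hourly sampling over 34 hours: 34 / 2 = 17 draws, or 18 with baseline.
- Scaled volume: 168 × 17/22 = 129.8 ml, or 168 × 18/23 = 131.5 ml.

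Section 6.1 says "the amount of blood taken on that visit would be approximately 130 ml (8.8 tablespoons"). The agreement supports reading 504 ml as the total for three visits. With two intervals of 13 ± 2 days, Visits 1 to 3 span about 22 to 30 days.

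**3. The limits as written.**

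- Women: 11.0 / 1000 = 0.011 g/dL.
- Men: 12.5 / 1000 = 0.0125 g/dL.
- If the numerals are meant in g/dL, they equal 11,000 and 12,500 mg/dL, so the ratio is exactly 1000.

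**4. Who is excluded?** The haemoglobin values below are illustrative assumptions; the documents give none.

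| Haemoglobin, g/dL | In mg/dL | Below the limit as printed | Below the numeral read in g/dL |
|---|---|---|---|
| 5 | 5,000 | No | Both sexes |
| 9 | 9,000 | No | Both sexes |
| 10.9 | 10,900 | No | Both sexes |
| 12.4 | 12,400 | No | Men only |
| 15 | 15,000 | No | Neither |

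**5. Does the unit reach the 10% rule?** The rule compares (screening − visit) / screening with 0.10. Multiplying both values by 1000 leaves the ratio unchanged, so it does not.

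**6. Do the other provisions replace the fixed limit?** History does not detect anaemia that was never diagnosed. Physician discretion has no stated number. The 10% rule is relative: a person at an assumed 9 g/dL at screening and again at Visit 2 has a fall of 0% and does not trigger it. The rule also reduces sampling and does not exclude, and the first repeat count comes at Visit 2, after the Visit 1 draws of about 168 ml.

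**The case against.** The strongest reply is that this is an obvious unit slip. A limit of 0.011 g/dL is so implausible that clinical staff would recognise it and read g/dL. That stands, and it is why the practical weight is small.

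Three stronger readings are tempting, and the documents do not support them:

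- A reader might infer that an eligibility form carrying these figures would never flag anyone. This does not follow. If the laboratory reports in g/dL, a form that compares the reported numeral with 11.0 or 12.5 flags a woman at 10.5 and a man at 12.4. It stays silent only if values are first converted to mg/dL. The documents describe no such conversion and no automated eligibility check; Section 8.3 mentions electronic case report forms only in general terms.
- A reader might infer that, apart from this limit, only medical history guards against enrolling an anaemic person. Section 4.4 separately allows exclusion on any blood result that the study physician finds unacceptable, and also where the investigator considers participation unsafe.
- A reader might infer that the error carries through to the 10% rule. That rule is a ratio to the participant's own screening value, so the unit cancels.

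It is also fair to say that 534 ml is not taken at once. It is spread over screening and three visits.

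**Conclusion.** The point holds in a limited form. Both limits are wrong by their printed unit, nothing elsewhere in the protocol corrects them, and read literally the fixed laboratory arm excludes 0% of candidates. That g/dL was meant, and hence the factor of 1000, is an inference from plausible haemoglobin values, because the documents name neither the intended unit nor the laboratory's reporting unit.

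The weight is minor. Correct reading by staff is likely, and the provisions that do not depend on the unit still offer protection, although none restores the fixed sex-specific limit. The documents do not show that anyone was wrongly enrolled or that any form carries the error. The primary endpoint, the target of ten men and ten women, the sampling schedule and the analysis are untouched.

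**What to change.** The sponsor should confirm the intended unit and correct it for both limits in Section 4.4 to the unit in which the screening laboratory reports haemoglobin, presumably g/dL. The eligibility case report form should carry the same unit next to the recorded value. The numeric cut-offs are a clinical matter and stay as they are.

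The cost is a one-word correction made in two places, plus a check of the form. No sample size, visit or analysis changes.

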sGLT2	Sodium-Glucose CoTransporter2.
SOP	Standard Operation Procedure
VGLUT	Vesicular Glutamate Transporters

Précis

Objective and Specific Aims: The objective of this proof-of-concept study is to demonstrate in non-diabetic men and women age ≥ 55 years that a sGLT2 inhibitor will increase ketone bodies and metabolites used for gluconeogenesis. We also hypothesize that sGLT2 inhibitor (empagliflozin) will increase circulating glucagon and fatty acids, decrease circulating amino acids, increase expression of receptors and mediators of ketone metabolism in plasma exosomes and change Magnetic Resonance Spectroscopy (MRS) brain metabolism measures.

Experimental Design and Methods: 10 men and 10 women will be recruited for this pilot study. Each eligible participant will have a screen visit (Visit 0) and three additional 2-day study visits (Visit 1-3). On Visits 1, 2 and 3, frequent blood sampling for β -hydroxybutyrate butyrate (β -OHB), acetoacetate, fatty and amino acids, glucagon, insulin and glucose levels will be carried out; these visits will also include blood work for exosome markers and brain MRS. In addition, placement of a continuous glucose monitor (CGM) along with a 34-hour urine collection will be carried out. On Visits 1 and 2 the participants will wear the CGM until they return for their next visit. On Visit 3 the CGM will be removed at the end of the study visit. On Visit 1, no empagliflozin will be administered. Participants will return in 13 +/- 2 days for Visit 2. Visit 2 is the same as Visit 1 except empagliflozin 25 mg will be administered both mornings, at least 30 minutes before eating breakfast and participants will continue empagliflozin 25 mg once every morning, at least 30 minutes before eating breakfast, at home until they return in 13 +/- 2 days for Visit 3. At the end of Visit 3, empagliflozin will be stopped.

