3.2 Study Endpoints

The primary study endpoint will be the level of circulating ketones on Visit 3 with a target of 1.5 times that of the participant's baseline (Visit 1). Other outcomes will be secondary.

4 Study Population

Twenty participants, ten males and ten females, age 55 and older will complete this pilot study. The ceiling for this study (100) reflects the additional accrual that we may anticipate. If needed, the protocol will be amended to account for an increase in the number of participants needed to be recruited.

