4.2 Recruitment Plan

Subjects will be recruited using multiple strategies, including but not limited to advertising in newspapers, flyers, Internet, NIH and NIA websites, expos and health fairs, volunteers who have expressed interest in NIA studies, and word of mouth from other study participants. All participants are recruited based on the same inclusion and exclusion criteria.

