Risks of Study Medication empagliflozin (Jardiance): The most common adverse reactions associated with administration of empagliflozin are dehydration, dizziness, lightheadedness, weakness, yeast and urinary tract infections. To decrease these risks, participants will be encouraged to hydrate and to maintain good hygiene. Other side effects may include low blood sugar, nausea, and upper respiratory tract infections. There also may be other side effects that we cannot predict, including hypersensitivity reaction. Rarely, sudden episodes of kidney injury may occur. Also, the Food and Drug Administration (FDA) has issued a warning about rare occurrences of a serious infection of the genital area (necrotizing fasciitis of the perineum) associated with sGLT2 inhibitors. Both of these have only been known in people who have diabetes. We will monitor for any symptoms during our daily calls to the participant while they are on study medication. This will include questioning any symptoms of tenderness, redness,

or swelling of the genitals or the area from the genitals back to the rectum. We will also monitor for fever or general feeling of being unwell.

Risks of Continuous Glucose Monitor (CGM): Potential risks include a slight skin irritation from the adhesive.

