Appendix I: Symptom Review

I.D.# - ____ **Date:** _____ **Time:** _____ **Visit #** _____

Do you have any of the following symptoms?

Symptom	Yes	No	Comment
Dizziness			
Lightheadedness			
Weakness			
Yeast infection (i.e. itching, burning, redness, smelly discharge from genital area)			
Genital infection: tenderness, pain, swelling, flu-like symptoms			
Burning on urination			
Nausea			
Vomiting			
Diarrhea			
Constipation			

Confusion			
Feeling shaky			
Increased hunger			
Decreased hunger			
Headache			
Irritability			
Palpitations			
Anxiety			
Coughing			
Sneezing			
Nasal congestion			
Runny nose			
Fever			
Sore throat			
Shortness of breath			
Other			

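### The yeast-infection exclusion in section 4.4 is worded for vaginal infection only, so it cannot operate in the ten men, although the protocol warns about, advises on and monitors yeast infection without limit by sex

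*Combined protocol and SAP*

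**What the plan says.** Section 4.4 of the combined protocol and SAP has one exclusion that names yeast infection: "History of recurrent or recent vaginal yeast infection". Section 4.2 states that "All participants are recruited based on the same inclusion and exclusion criteria". The précis says that "10 men and 10 women will be recruited for this pilot study", and section 4 repeats the split: "Twenty participants, ten males and ten females, age 55 and older will complete this pilot study".

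The risk text in section 7.1 is not divided by sex: "The most common adverse reactions associated with administration of empagliflozin are dehydration, dizziness, lightheadedness, weakness, yeast and urinary tract infections". Its mitigation is addressed to everyone: "To decrease these risks, participants will be encouraged to hydrate and to maintain good hygiene". The Visit 2 discharge instructions (Appendix F) repeat the hygiene advice, naming urinary and yeast infections, with no separate version for men and women. The single symptom form in Appendix I has the item "Yeast infection (i.e. itching, burning, redness, smelly discharge from genital area", which refers to the genital area and not to the vagina.

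**The concern.** The criterion appears intended to keep out people already prone to a reaction that the protocol calls common on this drug. As worded, it can do so in only one sex. Everywhere else the protocol treats the reaction as relevant to every participant.

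Two things are at stake, both modest. The first is screening: two people with the same relevant history are handled by different routes according to sex. The second is the last secondary objective in section 2.2, which asks whether this age group tolerates the drug class. A pooled account of genital infections would come from women selected by a named criterion and men for whom no such criterion exists.

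**Working it through.** The plan gives no calculated figure on this point, so the check compares the text. The only arithmetic is the share of the planned sample that the criterion cannot reach: 10 men / 20 participants = 50% (précis and section 4).

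**Step 1. Reactions listed as most common in section 7.1, against exclusions in section 4.4.**

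| Reaction in 7.1 | Matching history exclusion in 4.4 | Can apply to men? |
|---|---|---|
| Dehydration | Yes, with a one-year window | Yes |
| Urinary tract infection | Yes, if chronic | Yes |
| Yeast infection | Yes, vaginal only | No |
| Dizziness, lightheadedness, weakness | None | Not applicable |

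Of the three reactions that have a matching exclusion, yeast infection is the only one whose exclusion is confined to one sex.

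**Step 2. Is the limit explained?** Where section 4.4 intends men and women to differ, as with hemoglobin, it gives a value for each. Section 4.5 gives reasons for the exclusions on renal function, diabetes and BMI. It gives none for confining the yeast criterion to women.

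**Step 3. Could another criterion catch a man with this history?**
- *Chronic urinary infection* concerns a different site.
- *Active infection or fever* concerns a current state, and counts only if it could alter glucose metabolism.
- *Being healthy* (section 4.3) refers back to the exclusion list, so it adds no separate test.
- *Unacceptable blood or urine results* depend on the study physician's view and concern test results, not a past history.
- *Investigator opinion that participation is unsafe* could reach him, but it is discretionary and does not name the condition.

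**Step 4. Follow the plan literally for two otherwise eligible people with a recent genital yeast infection.** The woman, if the infection is vaginal, is excluded with no judgement required. The man meets no named exclusion, so his entry depends on the investigator's opinion.

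**Step 5. What is affected downstream?** Section 3.2 defines the primary endpoint as circulating ketones at Visit 3 relative to the participant's own baseline, which this criterion does not enter. Section 12 states no comparison between the sexes. Only screening and the pooled tolerability description remain.

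**The case against.** The strongest reply is that a criterion narrower than the risk list is not a contradiction. Three other reactions in the same sentence of section 7.1 have no exclusion at all, and sex-specific criteria are legitimate. The risk is also managed during treatment in everyone, through daily calls, the symptom form, hygiene advice and a follow-up call within a week. Much of this stands. It makes the point an unexplained mismatch in wording, not an error in the design. It does not explain why a criterion considered necessary for women has no counterpart for men, and monitoring on drug does not replace a rule on who enters.

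Four stronger readings are tempting, and the documents do not support them.

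- *The gap leaves men exposed to the serious perineal infection.* Section 7.1 does mention "a serious infection of the genital area (necrotizing fasciitis of the perineum) associated with sGLT2 inhibitors", but then says it has been known only in people with diabetes, and section 4.4 excludes diabetes. Nothing in the documents says that a history of yeast infection screens for it.
- *Men enter the study unscreened.* Sections 5.1 and 5.2 give every participant a telephone screen, a medical history and a physical examination. The questions asked are not shown, so it cannot be said that men are not asked. What can be said is that they have no automatic exclusion.
- *A comparison of the sexes would be biased.* No such comparison is planned; section 2.2 asks about the age group as a whole.
- *A probability can be put on enrolling an affected man.* The documents give no rate of prior genital yeast infection in men, and a history is not the same as an infection on treatment.

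**Conclusion.** The point holds as a minor inconsistency between the eligibility wording and the protocol's own risk and monitoring text. Its supportable size is that 10 of 20 planned participants (50%) cannot meet the criterion as written. For them, exclusion on this ground rests on discretion alone.

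The conclusion rests on two readings. One is that risk text with no limit by sex is meant for both sexes, although the protocol does not say so in as many words; the common symptom form and shared discharge advice support that reading. The other is that the limit to vaginal infection is unintended or at least unexplained. A stated reason from the sponsor would close the point. The primary endpoint, the sample size and every planned analysis are unaffected.

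**What to change.** Reconcile section 4.4 with section 7.1 and Appendix I in one of two ways.

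1. Word the criterion so that it can apply to both sexes, for example *genital* in place of *vaginal*, which matches the site named in Appendix I. Confirm that the question is put to men at the medical history already scheduled in section 5.2.
2. If the limit to women is intended, state the reason, for instance in section 4.5 alongside the other justified exclusions.

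Whichever is chosen, the sponsor could define *recurrent* and *recent* in the same edit. The criterion leaves both open, which affects how it is applied to women as well.

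The cost is a short wording change and one history question. The first option may add an occasional male screen failure; the second adds none. No visit, sample or analysis changes.
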